7.17.3 Relatedness of Adverse Events and Serious Adverse Events

Relationship of an AE or SAE to investigational product is to be determined by the investigator based on the following definitions (see [Table 7-3](#)).

Table 7-3 Adverse Event Relatedness

Relationship to Product(s)	Definition
Not Related	Unrelated to investigational product
Possibly Related	A clinical event or laboratory abnormality with a reasonable time sequence to administration of investigational product, but which could also be explained by concurrent disease or other drugs or chemicals.
Probably Related	A clinical event or laboratory abnormality with a reasonable time sequence to administration of investigational product, unlikely to be attributable to concurrent disease or other drugs and chemicals and which follows a clinically reasonable response on de-challenge. The association of the clinical event or laboratory abnormality must also have some biologic plausibility, at least on theoretical grounds.
Definitely related	The event follows a reasonable temporal sequence from administration of the investigational product, follows a known or suspected response pattern to the investigational product, is confirmed by improvement upon stopping the investigational product (de-challenge), and reappears upon repeated exposure (re-challenge). Note that this is not to be construed as requiring re-exposure of the subject to investigational product; however, the determination of definitely related can only be used when recurrence of event is observed.

7.17.4 Procedures for Recording and Reporting Adverse Events

7.17.4.1 Adverse Event Monitoring and Period of Observation

Adverse events will be monitored continuously. For the purposes of this study, the safety observation period will extend from the time of treatment with investigational product until the subject's final evaluation after treatment. For subjects who complete the study, the final evaluation of AEs will occur at the final follow-up visit performed 90 (\pm 7) days after treatment with investigational product.

If the investigator considers it necessary to report an AE in a subject after the end of the safety observation period, he or she should contact the sponsor to determine how the AE should be documented and reported.

7.17.4.2 Reporting Serious Adverse Events

Any SAE, regardless of relationship to investigational product, which occurs in a subject after informed consent, should be recorded by the clinical site on an SAE form. The SAE must be completely described on the subject's CRF, including the judgment of the investigator as to the relationship of the SAE to the investigational product.

The investigator will promptly supply all information identified and requested by the sponsor (or contract research organization [CRO]) regarding the SAE. The investigator must report the SAE to the Shire Pharmacovigilance and Risk Management Department AND to the Shire Medical Monitor on an SAE form. This form must be completed and faxed or emailed within 24 hours of the investigator's learning of the event to:

Shire Pharmacovigilance and Risk Management Department:

FAX: PPD [redacted] (Worldwide) OR PPD [redacted] (North America)

Email: PPD [redacted]

AND

Shire Medical Monitor: PPD [redacted] MD, MPH

PPD [redacted]

FAX: PPD [redacted] (USA)

Any follow-up information must also be completed on an SAE form and faxed or emailed to the same numbers listed above.

In the event of a severe and unexpected, fatal, or life-threatening SAE, the clinical site must contact the Shire Medical Monitor by telephone; this is in addition to completing and transmitting the SAE form as stated above. The following provides contact information for the Shire Medical Monitor.

If an SAE is assessed as severe and unexpected, or life-threatening, contact:

If an SAE is assessed as severe and unexpected, or life-threatening, contact:

PPD [REDACTED], MD, MPH
PPD [REDACTED]
Shire Orphan Therapies LLC
[name]
[name]
Telephone: PPD [REDACTED]
Mobile: PPD [REDACTED]
Fax: PPD [REDACTED] (USA)
PPD [REDACTED]

The investigator must promptly report all required information to the Institutional Review Board (IRB)/Independent Ethics Committee (IEC). It is the responsibility of the sponsor to ensure that each investigator receives a copy of any Council for International Organizations of Medical Sciences (CIOMS)/MedWatch report that has been submitted to the appropriate regulatory agencies notifying them of an unexpected related SAE.

The investigator or sponsor must ensure that the IRB/IEC receives a copy of the report and that a copy is also filed within their study files.

7.18 Pregnancy

Pregnancy and lactation are exclusion criteria for this study. The sponsor must be notified in the event of a pregnancy occurring during the course of the study and through the final follow-up visit after the subject's last dose of investigational product. Pregnancy is not to be reported as an AE; the pregnancy reporting form should be used to report the pregnancy. The pregnancy will be followed up through delivery or final outcome.

7.19 Abuse, Overdose, and Medication Error

Abuse – Persistent or sporadic intentional intake of investigational medicinal product at a dose higher than prescribed per protocol (but below the dose defined for overdose) or when used for non-medical purpose (eg, altering one's state of consciousness).

Misuse – Intentional or unintentional use of investigational medicinal product other than as directed or indicated at any dose, which is at or below the dose defined for overdose (Note: this includes a situation where the product is not used as directed at the dose prescribed by the protocol).

Overdose – No clinical information on overdose is available. A dose of 3.2 mg/kg (approximately 8 times the therapeutic dose) caused transient erythema, itching or hypotension in healthy subjects. No therapeutic intervention was necessary.

Medication Error – A mistake made in prescribing, dispensing, administration and/or use of the investigational medicinal product.

7.20 Removal of Subjects from the Trial or Investigational Product

A subject's participation in the study may be discontinued at any time at the discretion of the investigator. The following may be justifiable reasons for the investigator to remove a subject from the study:

- Non-compliance, including failure to appear at one or more study visits.
- The subject was erroneously included in the study.
- The subject develops an exclusion criterion.
- The subject suffers an intolerable AE.
- The study is terminated by the sponsor.
- The study is closed prior to the subject's first eligible attack.

The subject, the subject's parent(s), or the subject's legal guardian(s) acting on behalf of the subject is free to withdraw consent and discontinue participation in the study at any time without prejudice to further treatment.

If a subject or the subject's parent(s) or the subject's legal guardian(s) acting on behalf of the subject, discontinues participation in the study, or the subject is discontinued by the investigator, the subject completion/discontinuation CRF describing the reason for discontinuation must be completed. Any AEs experienced up to the point of discontinuation must be documented in the CRF. If AEs are present when the subject withdraws from the study, the subject will be re-evaluated within 30 days of withdrawal. All ongoing SAEs at the time of withdrawal will be followed until resolution.

7.20.1 Safety-Related Study Stopping Rules

The Data and Safety Monitoring Board (see Section 11.8 for a description of the DSMB and its role) may recommend to suspend the study until the DSMB can review any death that is drug or disease-related or unexplained, or if there is an unexpected drug-related severe AE.

Following the review of safety data, the study will be either:

- Resumed unchanged
- Resumed with modifications to the protocol
- Terminated

Subject safety will be monitored on a continuous basis during this study until the last subject completes his or her last scheduled study visit/assessment.

Additional information on safety monitoring can be found in Section 11.8.

7.21 Appropriateness of Measurements

The safety assessments used in this study are standard and will provide a detailed measure of the safety of icatibant in the pediatric population.

The measures of serum reproductive hormone concentration are accepted measures for assessing the function of reproductive organs.

Plasma samples will be assayed for concentrations of icatibant and its 2 major metabolites (M1 and M2) using a validated high-performance liquid chromatography/tandem mass spectrometry (LC-MS/MS) method with a lower limit of quantification of 1 ng/mL and a range from 1 to 1000 ng/mL (Analytical Report SHR10-002). Pharmacokinetic variables will be determined by full sampling and noncompartmental methods where possible, and elsewhere by sparse sampling (at least 4 to 7 time points) and a population PK approach using non-linear mixed effects modeling software.

The symptom score used in efficacy assessments in this study is an investigator-rated measure of symptom severity based on a standard 5-point scoring system (0-absence of symptoms, 1-mild, 2-moderate, 3-severe, 4-very severe) capturing symptoms of acute attacks of HAE that have been identified and validated to assess efficacy in adults. For attacks classified as abdominal or cutaneous, investigator-rated symptom scores are collected for 8 symptoms: abdominal tenderness, nausea, vomiting, diarrhea, skin pain, erythema, skin irritation, and skin swelling.

For attacks classified as laryngeal, investigator-assessed symptom scores are collected for 13 symptoms: abdominal tenderness, nausea, vomiting, diarrhea, skin pain, erythema, skin irritation, skin swelling, dysphagia, voice change, breathing difficulties, stridor, and asphyxia.

In all pediatric subjects in the present study, irrespective of age, the investigator-rated symptom score will provide an appropriate means to measure the severity of primary symptoms (eg, cutaneous and/or abdominal pain, cutaneous swelling, or laryngeal symptoms) of acute attacks of HAE at pretreatment and the change in symptom severity, if any, after treatment with icatibant.

Though subject-reported outcomes such as the symptom score and visual analog scale (VAS) have been employed successfully as efficacy measures in clinical studies of icatibant in adults, the use of these subject-reported outcomes in children poses special challenges. The Faces Pain Scale is a validated, self-reported measure used to assess the intensity of children's pain in a wide variety of clinical contexts (Bieri et al. 1990). The FPS-R was adapted from the original FPS in order to make it possible to score pain on a widely accepted 0-to-10 metric (Hicks et al. 2001). The scales are suitable for use in assessment of the intensity of children's acute pain from age 4 onward, are simple to administer, and require no specialized equipment other than the standardized images of faces. Use of the FPS-R is planned for this study, and will provide an appropriate means to measure pain associated with acute attacks of HAE in pediatric subjects who are at least 4 years of age.

Young children (ie, those below the age of 4 years) frequently lack the verbal and cognitive skills necessary to report physical discomfort and pain intensity. Behavioral cues are the primary indicators of pain in children who are unable to report pain or follow instructions in the use of assessment tools. The FLACC instrument comprises 5 categories of behavior (face, legs, activity, cry, and consolability) to assess pain in preverbal children or children with limited verbal capability (Manworren and Hynan 2003; Merkel et al. 1997). Each category is scored on a 0-to-2 scale which results in a total score from 0 to 10.

Collectively, the measures employed in this study are expected to allow for assessment of the PK profile, tolerability, safety, and efficacy of icatibant in the pediatric population.

8 STUDY ACTIVITIES

8.1 Screening (Day of Informed Consent to Pretreatment on Day 1)

- Informed Consent/Assent
- Inclusion/Exclusion Criteria
- Medical history
- Documentation of HAE attack(s) not treated with icatibant*
- Confirmation of documented HAE diagnosis (via the sponsor's central laboratory)
- Measurement of C1-INH
- Pubertal status determination
- Physical examination
- Vital signs
- ECG
- Height and weight
- Urine pregnancy test (in females of childbearing potential)
- Recording of concomitant medications

*For all subjects who remain enrolled in the study for longer than 6 months, a telephone contact will be scheduled every 6 months to collect information concerning HAE attacks not treated with icatibant in the study.

8.2 No Attack

8.2.1 Pretreatment (Baseline) Assessments (Day 1)

The following assessments will be performed for subjects who will be treated with icatibant in the absence of a current HAE attack. All evaluations and sample collections must be performed prior to treatment.

- Medical history
- Confirm inclusion/exclusion criteria
- Pubertal status determination (only if the subject was classified as prepubertal at the time of the screening visit)
- Menstrual cycle history (in pubertal/postpubertal females only)
- Physical examination
- Vital signs
- Height and weight
- Clinical laboratory tests (serum chemistry, hematology and urinalysis)
- Urine pregnancy test (in females of childbearing potential)
- Reproductive hormone assessments
- Pharmacokinetic sampling
- Immunogenicity evaluation
- Recording of concomitant medications

8.2.2 Treatment Period (Day 1 to Day 8 [± 1 Day])

- Investigational product administration (Day 1, Time 0)
- Physical examination (Day 1, 6 [±0.5] hours) (or 8 [±0.5] hours if the subject is not discharged^{***}) post dose and Day 8 [±1 day])
- Vital signs (Day 1, 1 hour [±10 minutes], 6 [±0.5] hours) (or 8 [±0.5] hours if the subject is not discharged^{***}) post dose and Day 8 [±1 day])
- ECG (Day 1, 6 [±0.5] hours (or 8 [±0.5] hours if the subject is not discharged^{***}) post dose)
- Clinical laboratory tests (Day 1, 6 [±0.5] hours post dose and Day 8 [±1 day])
- Reproductive hormone assessments (Day 1, 6 [±0.5] hours post dose and Day 8 [±1 day])
- Injection site reaction evaluation (Day 1, 1 hour [±10 minutes], 6 [±0.5] hours) (and 8 [±0.5] hours if the subject is not discharged^{**}) post dose, Day 2 (24 [±4] hours), Day 3 (48 [±4] hours), and Day 8 [±1 day])
- Sampling for PK assessments in pubertal/post pubertal subjects (Day 1, 15 [±5] minutes, 30 [±5] minutes, 45 [±5] minutes, 1 hour [±10 minutes], 2 hours [±10 minutes], 4 [±0.5] hours, 6 [±0.5] hours post dose)
- Safety follow-up contact (Day 2 (24 [±4] hours), Day 3 (48 [±4] hours) by telephone (If a subject remains hospitalized, this safety follow-up will be conducted in person.)
- Immunogenicity evaluation (Day 8 [±1 day])
- Menstrual cycle history (Day 8 [±1 day] in pubertal/postpubertal females)
- Recording of concomitant medications
- Assessment of AEs

*A subject may be discharged after completion of all assessments at 6 hours post treatment, if deemed medically stable in the investigator's clinical judgment. If this is the case, the assessments scheduled for 8 hours post treatment will be omitted.

8.3 Initial Icatibant-treated Attack

8.3.1 Pretreatment (Baseline) Assessments (Day 1)

The following assessments will be performed at the initial icatibant-treated attack. All evaluations and sample collections must be performed prior to treatment.

- Medical history
- Confirm inclusion/exclusion criteria
- Pubertal status determination (only if the subject was classified as prepubertal at the time of the screening visit)
- Menstrual cycle history (in pubertal/postpubertal females only)
- Physical examination
- Vital signs
- Height and weight
- Subject self-assessment of HAE-related pain (in subjects 4 years of age and older) using diary FPS-R
- Investigator assessment of HAE symptoms

- Investigator assessment of HAE-related pain (in subjects younger than 4 years of age only) using FLACC
- Clinical laboratory tests (serum chemistry, hematology and urinalysis)
- Urine pregnancy test (in females of childbearing potential)
- Reproductive hormone assessments
- Pharmacokinetic sampling
- Immunogenicity evaluation
- Recording of concomitant medications

8.3.2 Treatment Period (Day 1 to Day 8 [\pm 1 Day])

- Investigational product administration (Day 1, Time 0)
- Physical examination (Day 1, 6 [\pm 0.5] hours) (or 8 [\pm 0.5] hours if the subject is not discharged^{***}) post dose and Day 8 [\pm 1 day])
- Vital signs (Day 1, 1 hour [\pm 10 minutes], 6 [\pm 0.5] hours) (or 8 (\pm 0.5) hours if the subject is not discharged^{***}) post dose and Day 8 [\pm 1 day])
- ECG (Day 1, 6 [\pm 0.5] hours (or 8 [\pm 0.5] hours if the subject is not discharged^{***}) post dose)
- Subject self-assessment of HAE-related pain (in subjects 4 years of age and older) using diary FPS-R (Day 1, 1 hour [\pm 10 minutes], 2 hours [\pm 10 minutes], 4 [\pm 0.5] hours, 6 [\pm 0.5] hours and 8* [\pm 0.5] hours post dose, Day 2 (24 [\pm 4] hours), Day 3 (48 [\pm 4] hours))
- Investigator assessment of HAE symptoms (Day 1, 1 hour [\pm 10 minutes], 2 hours [\pm 10 minutes], 4 [\pm 0.5] hours, 6 [\pm 0.5] hours (and 8 [\pm 0.5] hours if the subject is not discharged^{**}) post dose)
- Investigator assessment of HAE-related pain (in subjects younger than 4 of age only) using FLACC (Day 1, 1 hour [\pm 10 minutes], 2 hours [\pm 10 minutes], 4 [\pm 0.5] hours, 6 [\pm 0.5] hours (and 8 [\pm 0.5] hours if the subject is not discharged^{**}) post dose)
- Clinical laboratory tests (Day 1, 6 [\pm 0.5] hours post dose and Day 8 [\pm 1 day])
- Reproductive hormone assessments (Day 1, 6 [\pm 0.5] hours post dose and Day 8 [\pm 1 day])
- Injection site reaction evaluation (Day 1, 1 hour [\pm 10 minutes], 6 [\pm 0.5] hours (and 8 [\pm 0.5] hours if the subject is not discharged^{**}) post dose, Day 2 (24 [\pm 4] hours), Day 3 (48 [\pm 4] hours), and Day 8 [\pm 1 day])
- Sampling for PK assessments in pubertal/post pubertal subjects (Day 1, 15 minutes [\pm 5 minutes], 30 minutes [\pm 5 minutes], 45 minutes [\pm 5 minutes], 1 hour [\pm 10 minutes], 2 hours [\pm 10 minutes], 4 [\pm 0.5] hours, 6 [\pm 0.5] hours post dose at initial attack only)
- Sampling for PK assessments in prepubertal subjects (Day 1, 15 minutes [\pm 5 minutes], 30 minutes [\pm 5 minutes], 2 hours [\pm 10 minutes], 4 [\pm 0.5] hours, 6 [\pm 0.5] hours post dose at initial attack only)
- Safety follow-up contact (Day 2 (24 [\pm 4] hours), Day 3 (48 [\pm 4] hours) by telephone (If a subject remains hospitalized, this safety follow-up will be conducted in person.)
- Immunogenicity evaluation (Day 8 [\pm 1 day])
- Recording of concomitant medications
- Assessment of AEs

*A subject may be discharged after completion of all assessments at 6 hours post treatment, if deemed medically stable in the investigator's clinical judgment and the subject's HAE symptoms have resolved (the subject's investigator-rated symptom score = zero, denoting the absence of symptoms).

If this is the case, the assessments scheduled for 8 hours post treatment will be omitted with the exception of subject self-assessment of HAE-related pain using the diary FPS-R.

**If the subject's HAE symptoms have not resolved at 6 hours post treatment (the subject's investigator-rated symptom score \neq zero) and the subject is not to be discharged after completion of assessments at the 6-hour time point, the assessments indicated will be performed at both 6 AND 8 hours post treatment.

***If the subject's HAE symptoms have not resolved at 6 hours post treatment (the subject's investigator-rated symptom score \neq zero) and the subject is not to be discharged after completion of assessments at the 6-hour time point, the assessments indicated will be performed at either 6 OR 8 hours post treatment.

8.3.3 Follow-up Visit (Day 90 \pm 7 days)

In the event that a subject has a subsequent HAE attack within the 90 day follow-up period for the first treatment, the date of the Day 90 follow-up visit for the first treatment remains the same. Each subsequent treatment will have a corresponding Day 90 follow-up visit.

- Physical examination
- Vital signs
- Height and weight
- Clinical laboratory tests (serum chemistry, hematology, and urinalysis)
- Urine pregnancy test (in females of childbearing potential)
- Reproductive hormone assessments
- Immunogenicity evaluation
- Menstrual cycle history (in pubertal/postpubertal females)
- Recording of concomitant medications
- Assessment of AEs
- Documentation of HAE attack(s) not treated with icatibant

8.3.4 Telephone Contact (Month 6 \pm 7 days)

The scheduled telephone contact will document pubertal changes/milestones, if any.

- Pubarche
- Menarche (females only)
- Changes in menstrual cycle (females only)
- Pregnancy (females and male partner)

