4.2 Rationale for Study Design

This study has an open-label, single arm design.

The study is intended to determine the PK profile of SC icatibant when administered to children and adolescents with HAE and to identify an optimal pediatric dosing regimen.

In addition, the study is intended to establish the tolerability and safety of icatibant in children and adolescents, particularly with respect to potential effects on reproductive development, and to demonstrate the effectiveness of icatibant in relieving the symptoms of acute HAE attacks. Therefore, this study will help determine whether icatibant can address an unmet medical need for a safe and effective treatment for acute attacks of HAE in pediatric patients.

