Safety Follow-up Contact												X ^c	X ^c			
Injection Site Reaction Evaluation							X			X	X ^e	X ^c	X ^c	X		
PK Sampling ^d		X		X	X	X	X	X	X	X						
Immunogenicity Evaluation		X												X	X	
Concomitant Medications	X	X	X	X	X	X	X	X	X	X	X ^e	X ^c	X ^c	X	X	
Adverse Events			X	X	X	X	X	X	X	X	X ^e	X ^c	X ^c	X	X	

(Pubertal/postpubertal subjects only)	Screening Period	Pre-treatment (Baseline)	Treatment	Post Treatment										Follow-up				
				Day 1										Day 2	Day 3	Day 8 (±1)	Day 90 (±7)	Month 6 (±7 days) Telephone Contact
Study Day		Day 1	Day 1															
Time Post Treatment (hours)			0	0.25	0.5	0.75	1	2	4	6	8	24	48					
Window (hours or minutes)				(±5) min	(±5) min	(±5) min	(±10) min	(±10) min	(±0.5) hr	(±0.5) hr	(±0.5) hr	(±4) hr	(±4) hr					
Assessments																		

Abbreviations: FLACC = Faces, Legs, Activity, Cry, and Consolability (comportmental pain scale); FPS-R = Faces Pain Scale-Revised; FSH = follicle stimulating hormone; HAE = hereditary angioedema; hr = hour; LH = luteinizing hormone min = minute; PK = pharmacokinetic; SC = subcutaneous

- ^a The inclusion/exclusion criteria will be confirmed at the Pretreatment (Baseline) Visit.
- ^b A subject’s classification as prepubertal or pubertal/postpubertal will be determined at the Day 1 pretreatment visit. Note that a subject classified as pubertal/postpubertal at screening will not require further evaluation of pubertal status during the study.
- ^c These assessments may be conducted by telephone contact.
- ^d The PK sampling times shown are for pubertal/postpubertal subjects.
- ^e A subject may be discharged after completion of all assessments at 6 hours post treatment, if deemed medically stable in the investigator’s clinical judgment. If this is the case, the assessments scheduled for 8 hours post treatment will be omitted.
- ^f For all subjects who remain enrolled in the study for longer than 6 months, a telephone contact will be scheduled every 6 months to collect information concerning HAE attacks not treated with icatibant in the study.

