^a DO NOT use development of pubertal hair as evidence of progression to Tanner stage II because this could reflect increased adrenal gland function (adrenarche) in prepubertal subjects and not hypothalamic/gonadal function. The descriptions used in this table are intended to provide guidance for the investigators and may not align with descriptions of pubic hair and pubertal stage in other sources.				

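### After dosing, no examination repeats pubertal stage and the Month 6 call asks boys only about pubarche, so clinical pubertal progression is not directly measured

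*Protocol*

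**What the plan says.** Protocol Section 4.2 sets out to establish safety "particularly with respect to potential effects on reproductive development". Section 11.8 gives the role of bradykinin B2 receptors in reproductive development as the reason for an external DSMB. Section 1.2.3 describes nonclinical effects on sexual organs and maturation, including reproductive tissue findings in male rats.

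One clinical follow-up is aimed at puberty, the telephone contact at Month 6: "The scheduled telephone contact will document pubertal changes/milestones, if any". Section 8.3.4 lists four items: pubarche; menarche (females); menstrual cycle changes (females); and pregnancy, in a female subject or a male subject's partner.

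Appendix 4 defines the stages. Its footnote tells investigators "DO NOT use development of pubertal hair as evidence of progression to Tanner stage II", because hair growth may be adrenal in a prepubertal child. The stage 2 signs left are the breast bud in girls and enlargement of the scrotum and testes in boys.

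Section 4.1.2 has pubertal status determined at screening and, for those prepubertal then, reassessed at the first treated attack. Section 8.3.1 places that reassessment before dosing. Footnote b of Appendix 1 adds that a subject already pubertal/postpubertal at screening "will not require further evaluation of pubertal status during the study".

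SAP Section 7.9.7 counts hormone values outside a normal range specific to sex and pubertal status.

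**The concern.** The Month 6 call exists to pick up pubertal milestones, and Section 4.3 keeps the study open until the required subjects have reached that follow-up. For a boy, its only developmental item is the sign that Appendix 4 sets aside for staging. If no examination after the dose fills the gap, a boy dosed while prepubertal could reach Tanner II, or not, with no clinical record of it.

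There is a second effect on the hormone analysis. If the range depends on pubertal status and status is fixed before the dose, a child who enters puberty before the Day 90 sample may be compared with the wrong range.

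**Working it through.** The plan states no figure for pubertal progression, and Section 10.2 says that the sample size is empirical. The check is therefore a count of what is scheduled, with the passages set side by side.

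**Step 1. Month 6 items by sex (Section 8.3.4).**

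| Item | Boys | Girls | Appendix 4 stage 2 sign? |
|---|---|---|---|
| Pubarche | yes | yes | no, excluded by the footnote |
| Menarche | no | yes | no, but a gonadal milestone |
| Menstrual change | no | yes | no, but gonadal |
| Pregnancy | partner only | yes | no, not a stage of puberty |

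Gonadal milestones asked: 0 for boys; 2 for girls, of which only menarche can come first in a girl who was prepubertal at dosing. Appendix 4 stage 2 signs asked (breast bud, testicular or scrotal enlargement): 0 in either sex.

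**Step 2. Staging after a dose.** In Appendices 1 and 2 the pubertal status row is marked at screening and at Day 1 pretreatment only. Appendix 3 has no such row. The visit lists in Sections 8.2.2, 8.3.2, 8.3.3 and 8.4 agree, as does SAP Appendix III. Stagings after dosing: 0 in all three schedules.

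**Step 3. Could another examination capture it?** The physical examination in Section 7.13.1 has nine elements, none of them breast or genital. The Day 90 physical examination does not supply stage incidentally.

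**Step 4. What does bear on reproductive development.** Boys have FSH, LH and testosterone at pretreatment, 6 hours, Day 8 and Day 90 of the initial treatment, which is 3 samples after the dose. For each subsequent attack they are measured at baseline, Day 8 and Day 90, which is 2 after the dose. Prepubertal subjects receive one dose, so their last scheduled hormone sample is Day 90; the Month 6 call has none. Girls also have menstrual history at Day 90.

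**Step 5. The hormone ranges.** SAP Section 7.9.7 needs a pubertal status for each sample, and by Step 2 the only status collected is from screening or Day 1. The SAP does not say which status it will use. If the ranges have two classes, the problem is confined to children prepubertal at dosing (at least 10 planned) who enter puberty by Day 90. If the ranges go by individual Tanner stage, it extends to older subjects too. The documents do not say which.

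**Step 6. Outputs.** The SAP's lists of tables, figures and listings include menstrual cycle history (Listing 16.2.8.10), but nothing that reports Month 6 milestones or a change in pubertal stage.

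**The case against.** The strongest reply is that the study's chosen measure is hormonal. The objectives name reproductive hormone levels, Section 3.1 puts them in the primary safety endpoint, and Section 7.21 calls them accepted measures of reproductive organ function. They reflect the gonadal axis that Appendix 4 distinguishes from adrenarche. No objective or endpoint names pubertal progression or Tanner change. This stands. A reader might infer that an effect on reproductive development could not be seen at all in boys; the documents do not support that.

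A reader might also infer that Appendix 4 contradicts Section 8.3.4 or makes pubarche worthless. It does neither. The footnote is a rule for assigning Tanner II and does not bar recording pubarche. The fault is that nothing acceptable for staging is asked beside it.

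Third, the study has a single arm and plans at least 10 prepubertal subjects, each dosed once. Restaging could describe progression but could not attribute it to icatibant without an external reference. That stands too, though the safety analysis is descriptive throughout.

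Last, Protocol Section 1.2.2 says that initial treatment is complete, and SAP Section 9.3 says that an interim analysis has been done. A change limited to the initial-treatment schedule could miss most of the children concerned. The documents do not say how many Day 90 visits or Month 6 calls remained.

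**Conclusion.** The narrower point holds. In boys the Month 6 call records no milestone that Appendix 4 accepts for entry to Tanner II, breast budding is not asked of girls, and stage is never redetermined after dosing. Clinical pubertal progression is not directly measured; hormones to Day 90, with menarche and menstrual data in girls, are the remaining evidence.

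This is a limitation worth repairing. It does not invalidate the primary safety endpoint, and it would be wrong to say that neither an effect nor its absence could be judged from any data collected. Entry to Tanner II concerns the subjects prepubertal at dosing, planned as at least 10. The number of boys among them is not given; if exactly 10 are enrolled, it lies between 0 and 10.

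The point about hormone ranges rests on an assumption: that the SAP will apply the pre-dose status, the only one scheduled, to later samples.

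**What to change.** - **Day 90 of the initial treatment (Appendix 2):** add Pubertal Status Determination, by Appendix 4 breast or genital criteria, for subjects prepubertal at dosing.
- **Visits still running (Appendix 3):** add it to the remaining 6-monthly baseline and Day 90 visits. Record the Tanner stage itself. Section 7.8 asks only for prepubertal or pubertal/postpubertal, and everyone treated under Appendix 3 is already in the second class.
- **Month 6 call (Section 8.3.4):** ask about breast budding in girls and testicular or scrotal enlargement in boys. Report pubarche separately as a possibly adrenal sign.
- **SAP:** add a listing or shift table of stage and Month 6 milestones. In Section 7.9.7, use the stage at the time of sampling for the hormone reference range; where none was recorded, name the status used.
- **Reporting:** call the results descriptive, and state the limitation for subjects already past these contacts.

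The cost is a revised telephone script, one added output, and a short but sensitive examination element at visits that already take place. That element is new, because the listed physical examination does not include it. A family's report by telephone is less reliable than an examination, so the Day 90 staging should carry more weight than the call.
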